4. a. To assess if variability in physical therapy milestones post-op is associated with flare at 6 weeks
 - b. To assess if variability in physical therapy milestones post-op is associated with patient reported outcome measures at 1 year (for e.g., HAQ, DAS-28, HOOS, KOOS).
5. To evaluate if RA patients who flared within 6 weeks after arthroplasty exhibit an increase in ROCK activation at 6 weeks over and above pre-operative baseline levels, compared with patients who don't flare.
6. To better understand the molecular signature of RA flare and prodrome to RA flare. Blood samples harvested during various states of RA disease activity will be analyzed by RNA sequencing and Luminex® protein array to establish which pathways fluctuate most during disease worsening as well as prodrome to worsening. RA flare and the prodrome to flare will be measured by patient self-report using validated instruments of patient reported prodromal symptoms, patient reported disease activity measures and the OMERACT PFQs.

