Little is known about the characteristics or rate of flare in the post-operative period, and little is known about the impact of post-operative flare on either overall disease status or arthroplasty outcome. We have shown that RA patients who undergo THR have worse outcomes at two years in WOMAC pain and function scores compared to OA controls ([name] EULAR 2013), but the reasons for this disparity are not understood. To minimize risk of infection, biologic agents are discontinued perioperatively. It is not known if increases in flare contribute to worse THR outcomes in RA patients relative to OA patients but post-operative flare needs to be considered as a likely factor. If RA patients who flare are unable to participate in postoperative rehabilitation regimens which are important in optimizing arthroplasty outcomes, they may not achieve optimal outcomes. In particular domains that worsen with flare such as fatigue and difficulty coping and participating, conceivable could contribute to a worse outcome. Paradoxically, while patients with multiple arthritic joints have worse outcomes after arthroplasty compared to patients with a singly affected joint (5), which may explain the worse outcome for RA THR patients, RA TKR patients do equally well as osteoarthritis controls, ([name] EULAR 2013). Thus factors other than polyarticular joint involvement must be impacting outcomes in RA patients undergoing THR. RA patients who have a prolonged or difficult time in re-establishing low disease activity or remission may have worse arthroplasty outcomes and this may be associated with worsening of the flare domains of joint pain and swelling, reflected by escalation to polyarticular disease (6, 7).

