- Resulting number per group:

47 with effect size 16% (0.25-0.10) overall.

109 with effect size 11% (0.25-0.15) overall.

394 with effect size 6% (0.25-0.20) overall.

- Total sample size required:

47 patients will provide an adequate sample size to evaluate the primary outcome and enable explorations for the secondary outcomes in this study. It is anticipated that 20% will drop out of the study thus we will need to recruit 57 patients to this study to adequately study the primary and secondary outcomes in this study.

References

Fleiss, J. L., Levin, B., Paik, M.C. 2003. Statistical Methods for Rates and Proportions. Third Edition. John

Wiley & Sons. New York.

Lachin, John M. 2000. Biostatistical Methods. John Wiley & Sons. New York.

Edition. Blackwell Science. Malden, Mass.

Zar, Jerrold H. 1984. Biostatistical Analysis (Second Edition). Prentice-Hall. Englewood Cliffs, New Jersey.

3.0

Data Analysis: describe how the primary outcome will be analyzed and what types of statistical calculations will be used. Do the same for each secondary outcome. Reiterate briefly the main analysis to be done, which groups, which variables, possible confounders. Address how possible confounders will be identified and handled in analysis:

For the Primary Outcome:

Descriptive statistics (rates and proportions, frequency distributions, means, medians, standard deviations and inter-quartile ranges) will be used to describe the baseline data. The two-tailed unpaired Student's t test, or Kruskal-Wallis tests will be performed to evaluate differences in continuous variables between groups (Flare vs. non-Flare group), depending on the distribution of the data, and the Scheffe or Bonferroni multiple comparisons test will be used for multiple comparisons. Chi-Square or Fisher's exact test will be utilized here to compare proportions between groups. Logistic regression will be performed for the HOOS and KOOS score to adjust for potential confounders and effect modifiers.

All secondary outcomes are exploratory.

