Pending the distributions of the data, in aim 2 we will evaluate the standard mean difference or effect size for each domain (WOMAC, DAS-28, Flare questionnaire (pain, Pt global, stiffness, fatigue, coping, participation, Pt reported TJC, SJC) in patients who flare vs. those who do not based on criteria of DAS28 worsening, patient reported worsening, MD global, need to initiate or escalate treatment. We would also explore differences in long term WOMAC scores and biomarkers stratifying by flare and adjusting for unknown confounders including baseline function, age, sex, and co-morbidity score. Standard statistical tests will be used.

In aim 3 we will examine a limited number of predictors of flare within 6 weeks using appropriate statistical methods by using a generalized estimating equation and will adjust for unrecognized confounders/effect modifiers including long term WOMAC scores, baseline function, age, sex, and co-morbidity score, and biomarkers stratifying by flare. Standard statistical tests will be used.

In aim 4 we aim to determine how patients who flare meet physical therapy milestones including walking distance, and ADLs, in comparison to patients who do not flare. The evaluation of meeting physical therapy milestones is exploratory. Physical therapy milestones are routinely evaluated as post-op TJA measures and are done weekly. We will examine the distributions of change for each covariate recorded by physical therapy and compare changes in each domain stratified by flare vs. no-flare.

A potential analytic plan depending on distribution of the final data to assess PT milestones will include:

Physical therapy milestones will be assessed based on the questionnaire and analyzed as outlined below: patient VAS: continuous variable- ranging from 0 ~100, analyzed with T-test or regression

Change will be analyzed by

- 1- ANCOVA and study of change
- 2- GEE and treat delta as our continuous outcome

Walking distance: Ordinal variable - Chi-square, fisher exact

Stairs/Transfers/Activities/Driving/Employed: Nominal- Chi-square, fisher exact

We will also explore whether or not the meeting of PT milestones impacts pain and function at 1 year using the HOOS/KOOS. We will treat PT milestones as a binary and WOMAC outcomes will be analyzed as predictors.

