In aim 5 and 6 we will compare levels of serum and tissue biomarkers between RA who flare and RA who do not flare using T-tests or chi-square tests, as appropriate. We will correlate self-report functional scores and biomarkers with the development of flare using Spearman correlations.

After sequencing, the reads will be processed by the New York Genome Center in a dedicated RNA-Seq pipeline, consisting of ribosomal RNA filtering, genome mapping with STAR, various QC metrics obtained with picard tools and transcript quantification with HTSeq-count. The raw read counts will then be processed with one of the Bioconductor package for Differential Gene expression (DESeq, edgeR, or limma/voom).

[Help](#)

ID: 2014-233

View: 2.4 Consent Information

[Help](#)

Consent Information

1.0 Describe how, when, and where the consent process will be initiated:

If possible, before coming in to the hospital (either for a pre-operative visit or their surgery), patients will be called by a research team member to discuss the study and evaluate their interest in participating. Patients who are interested will then be consented prior to surgery by the study research assistant or their treating surgeon, or rheumatologist either in the office, in pre-surgical screening, or in the pre-op holding area. If convenient, patients can additionally review the study protocol with the coordinator over the phone, but they will always be consented in person. The consent will be placed in the patients' hospital chart.

In the event that a potential participant requires a translator and is scheduled to have surgery on a weekend, a co-investigator of the research study can contact the potential participant prior to the day of their surgery and consent the patient over the phone. The Hospital for Special Surgery's Language Services Phone Interpreter or in-house employee will translate the Informed Consent to Participate in a Research Study Involving Genetic Testing, the Short Form Consent, and the Research Authorization Form. The translator would function as the witness to the consenting process. If the participant agrees to enroll, the participant will sign these forms in person on the day of their first study visit.

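### Aim 4b models the 1-year score as a predictor of the milestone, and aim 5 tests biomarker levels although its question is change from baseline

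*Combined protocol and SAP*

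**What the plan says.** All analysis text below is in the combined protocol and SAP, View 2.11.1, item 3.0 (Data Analysis). Aims and hypotheses are in View 2, items 2.0 and 3.0.

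- **Aim 4b.** The aim is "To assess if variability in physical therapy milestones post-op is associated with patient reported outcome measures at 1 year". The analysis section restates it: "We will also explore whether or not the meeting of PT milestones impacts pain and function at 1 year using the HOOS/KOOS". The next sentence gives the model: "We will treat PT milestones as a binary and WOMAC outcomes will be analyzed as predictors".
- **Aim 5.** The aim asks whether patients who flare "exhibit an increase in ROCK activation at 6 weeks over and above pre-operative baseline levels", compared with those who do not. For aims 5 and 6 the plan is: "we will compare levels of serum and tissue biomarkers between RA who flare and RA who do not flare using T-tests", with chi-square as the alternative. Secondary outcome 5 (View 2, item 5.0) has the blood markers measured pre-operatively, at 6 weeks and at 1 year, and synovial tissue taken once, at surgery.
- **Walking distance.** "Walking distance: Ordinal variable - Chi-square, fisher exact".
- **HOOS/KOOS.** In the paragraph headed for the primary outcome: "Logistic regression will be performed for the HOOS and KOOS score to adjust for potential confounders and effect modifiers". No cut-point is given.

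The same section calls all secondary outcomes exploratory and describes the physical therapy (PT) analysis as a potential plan that depends on the data.

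**The concern.** The aim 4b model makes the 1-year score explain a milestone reached earlier in recovery. It gives no estimate of how much better or worse pain and function are at 1 year in patients who met their milestones, which is what the investigators want to know. The instrument named is also not the one collected.

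The aim 5 test can be significant when nothing changed differently. If patients who flare already have higher marker levels before surgery, a comparison of 6-week levels picks up that gap. The protocol itself expects such gaps: aim 3 tests ROCK-pathway molecules as baseline predictors of flare, and hypothesis 3 expects worse baseline disease activity in patients who flare. A positive aim 3 would therefore tend to produce a positive aim 5 without any extra rise, and it would be reported as immune activation during flare.

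**Working it through.** **The plan's own figure.** The only power figures concern the primary flare rate. An equal-tailed exact binomial test with N = 47 and P0 = 0.26 rejects at 6 or fewer, or 19 or more, flares. This gives alpha 0.0445 and power 0.8143 at P1 = 0.10, as printed. The rows for 109 and 394 also reproduce. Nothing below changes them, and the documents give no figure for aims 4 or 5.

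**Aim 4b, side by side.**

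| Place | Exposure | Outcome |
|---|---|---|
| Aim 4b | PT milestones | patient-reported measures at 1 year |
| Hypothesis 4 | flare | HOOS, KOOS, elbow or shoulder score at 1 year |
| Restated question in Data Analysis | meeting PT milestones | pain and function at 1 year (HOOS/KOOS) |
| Planned model | WOMAC | PT milestone (binary) |

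The first three rows agree that the 1-year score is the outcome; the fourth reverses it. WOMAC is absent from the secondary outcomes and from the questionnaires in Views 2.6 and 2.7, which list HOOS/KOOS.

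**Aim 5, illustration.** The group sizes follow from the plan: 0.26 × 47 = 12.2, so about 12 flare and 35 non-flare. The gap, effect and correlations are assumptions: marker SD = 1, baseline-to-6-week correlation ρ = 0.5 or 0.7, two-sided 5%.

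The standard error factor is √(1/12 + 1/35) = 0.3345.

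*No extra rise, baseline gap 0.5 SD that persists:*
- Levels t-test: noncentrality 0.5/0.3345 = 1.49 on 45 df, so it rejects in 31%.
- Change score: the true difference in change is 0, so it rejects in 5%.
- ANCOVA on the baseline level: the expected adjusted difference is 0.5 × (1 − ρ), that is 0.25 at ρ = 0.5 and 0.15 at ρ = 0.7. By simulation it rejects in 13% and 9%.

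*True extra rise of 0.8 SD, equal baselines:*
- Levels: noncentrality 0.8/0.3345 = 2.39, power 65%.
- Change: SD of change = √(2(1 − ρ)), which is 1.00 at ρ = 0.5 and 0.775 at ρ = 0.7. Noncentrality is 2.39 and 3.09, power 65% and 86%.
- ANCOVA (simulated): 77% and 90%.

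At ρ = 0.5 the change score has no more power than the levels test; at ρ = 0.3 it has less (51% vs 65%, simulated). The case for it is that it answers aim 5, not that it always has more power.

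**Walking distance, illustration.** Same 12 vs 35, proportional odds, equal category probabilities in the non-flare group, 4,000 simulated trials per case:

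| Levels | Odds ratio | Chi-square power | Rank-sum power |
|---|---|---|---|
| 3 | 3 | 29% | 38% |
| 4 | 3 | 26% | 43% |
| 5 | 3 | 22% | 43% |
| 3 | 5 | 55% | 66% |
| 4 | 5 | 51% | 71% |
| 5 | 5 | 45% | 73% |

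With no true difference both tests reject in about 5%. The cost of chi-square is about 10 to 28 points of power.

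**The case against.** The strongest defence is that these analyses are exploratory and the PT list is only a potential plan. Parts of the section also come closer to the questions. ANCOVA and GEE on change are named for PT measures. Long-term scores and biomarkers are to be compared by flare with adjustment for baseline function, age, sex and comorbidity. Aim 4b is worded as an association, and a milestone-on-score model still tests whether the two are associated.

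This lowers the severity but leaves both mismatches. The change methods are not assigned to the biomarkers, and the named adjusters do not include the pre-operative marker level. A reversed model may detect an association, but it does not estimate the 1-year difference that the plan asks about.

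Some stronger readings are tempting and are not supported:

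- **That chi-square on walking distance is invalid.** It keeps its type I error; it only ignores the ordering.
- **That the logistic sentence is simply wrong and should go.** It stands under the primary outcome, and hypothesis 3 lists baseline HOOS and KOOS as features of patients who flare. It may mean flare as the response with those scores as covariates. Since no cut-point is proposed, no loss from dichotomising can be computed.
- **That ANCOVA is the one correct method for aim 5.** Flare groups are not randomised. With a persisting baseline gap and no extra rise, ANCOVA also rejects above 5%, because it asks a conditional question. It holds 5% when the 6-week gap has shrunk to ρ times the baseline gap, but then the true changes differ: flare patients rise less.
- **That surgical joint must be an adjuster.** The Background says hip outcomes in RA are worse than in osteoarthritis, while "RA TKR patients do equally well as osteoarthritis controls". But joint is essentially constant within a HOOS model or a KOOS model; it matters only if the scores are pooled.

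**Conclusion.** The point holds for two analyses, which are wrong as written: the aim 4b model runs against its own question and names an uncollected instrument, and the aim 5 levels test does not test the increase over baseline. The walking-distance test is a minor loss of efficiency, and the logistic sentence is an ambiguity to clear up.

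For aim 5, under the assumed values, the false-signal rate is about 31% for levels, 5% for a change score and 9 to 13% for ANCOVA. These figures rest on a 0.5 SD baseline gap that persists, correlations of 0.5 to 0.7, and a 12 vs 35 split. The split does not apply to aim 4b, which contrasts milestone met with not met. The levels comparison remains right for synovial tissue, which has one time point.

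A reader might infer that the main result is at risk. It is not: neither the primary flare rate nor the sample size depends on these analyses. The point should be fixed before analysis but is not critical.

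**What to change.** 1. **Aim 4b.** Replace the model sentence with a linear regression of the 1-year HOOS (hip) or KOOS (knee) score on PT-milestone status, adjusted for the baseline score. Use one instrument name throughout; if a WOMAC score is to be derived from collected items, say how. Define the milestone window so that it closes before the 1-year score. Secondary outcome 4 gives 86 weeks of weekly PT data, which exceeds the one-year participation and must be reconciled.
2. **Aim 5.** For blood markers, compare the baseline-to-6-week change between flare and non-flare patients, with ANCOVA on the pre-operative level as the conditional alternative. State which estimand is meant. Keep the levels comparison for surgical tissue.
3. **Walking distance.** Use a rank-sum test or a proportional-odds model.
4. **Logistic sentence.** Name the response. If it is HOOS or KOOS, use linear regression; if it is flare, say so and keep the logistic model.
5. **Surgical joint.** Add it as an adjuster only if hip and knee scores are pooled.

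The cost is analysis wording, a little programming and one degree of freedom for the baseline covariate. No new data, visits or patients are needed.

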1.0 What is the condition or intervention to be studied?

The condition to be studied is worsening (flare) of rheumatoid arthritis (RA) in patients who have undergone arthroplasty. RA patients undergoing arthroplasty most often have severe, erosive disease. If the rate of flare approaches the estimated 26% rate suggested in a previous study for RA patients after arthroplasty (*Johnson ACR 2011*), this could be of significance in regards to their long term arthroplasty and disease outcomes. Patients who flare may not be able to participate in the post-operative rehabilitation thought necessary for optimal arthroplasty outcomes, and it may be difficult for patients who flare after

*Please click
Here for
example.*

discontinuing immunosuppressant medications for surgery to regain remission or low disease activity. Detailed clinical data collected longitudinally from RA patients with severe erosive disease undergoing arthroplasty in conjunction with further characterization of the molecular profile of blood and operative tissue could provide valuable information to inform best practices for this patient group.

2.0 What is/are the research question(s)/specific aim(s)? Pose very specific questions that can be addressed within the proposed design of the study. Prioritize them in order of importance.

1. To determine the rate of post-operative RA flare within 6 weeks of surgery, defined as
 - a. Worsening of disease activity, defined as an increase in the DAS-28 by 1.2 or by 0.6 if the DAS28 was ≥ 3.2 , OR
 - b. Patient reported worsening, defined as noting they are worse or much worse on the question rating their RA since pre-surgery
 - c. AND one of:
 - i. patient wants/needs retreatment of DMARDs and/or biologics and/or prednisone increase (or Medrol dose pack or equivalent or intra-articular corticosteroid injection)
 - ii. increase in MD global of 2/10
 - iii. increase in patient global of 2/10 (on the OMERACT Preliminary Flare Questions [PFQ])
 - iv. flare severity score of ≥ 10
2. To evaluate the responsiveness of the OMERACT PFQ in patients who flare, as defined as a worsening of DAS-28 by 1.2 or by 0.6 if the DAS28 was ≥ 3.2 OR by patient reported worsening.
3. To determine predictors of post-operative flare within 6 weeks of surgery such as baseline disease activity measures and biomarkers, including molecules in the Rho associated kinase (ROCK) pathway, which are measures of immune system activation

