3.0 What is/are the hypothesis(es)?

1. 26% of RA patients will flare after TJR, defined as
 - a. Post op increases in DAS28 > 1.2 if baselines < 3.2 or > 0.6 if baseline ≥ 3.2 OR
 - b. Are worse or much worse on question rating their RA since pre-surgery AND
 - c. Have at least one of
 - i. Want / need treatment
 - ii. An increase in MD Global of 2/10
 - iii. An increase in Patient Global of 2/10 (according to the definitions noted above)
2. The OMERACT preliminary flare questions (PFQs) will detect patients who flare as defined above.
3. RA patients who flare after TJR have worse baseline pre-operative disease activity (DAS >3.2), worse baseline function (HOOS, KOOS, HAQ, elbow/shoulder surveys) and more likely will have had a history of withdrawing a biological therapy compared to patients who do not flare.
4. RA patients who flare post op will not meet their physical therapy milestones and will have worse HOOS, KOOS, elbow, or shoulder pain and function outcomes 1 year after arthroplasty.
5. RA patients who flare will exhibit enhanced immune activation when baseline levels are compared to levels in patients who flare within 6 weeks of surgery based on increased expression/activation of ROCK, IRF4, IRF5 and IRF8 and decreased expression/activity of their inhibitors (Def6 and SWAP-70). These molecules participate in a biologic pathway that regulates production of pro-inflammatory cytokines, potential mediators of RA flare.
6. There is a discrete set of genes expressed in circulating monocytes in RA patients during flare and prodrome of flare.

4.0 Identify and define the primary outcome and when the outcome will be measured. If measuring change in post-operative function is the most important, that will be your primary outcome.

The primary outcome is rate of RA flare within 6 weeks of surgery as measured by the OMERACT flare questionnaire.

5.0 Identify and define the secondary outcome(s) and when they will be measured (list additional goals one at a time with their corresponding outcomes).

1. The severity and impact of flares, using the OMERACT PFQs in the post arthroplasty setting: PFQs including flare intensity, duration of flare and worsening of domains associated with flare (pain, fatigue, stiffness, patient

- reported tender and swollen joint count, difficulties with coping and participation).
- 2. DAS28 at baseline and post-op week 6, and the change during this interval.

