Many patients with RA who flare describe non-specific prodromal symptoms such as intense fatigue and flu-like symptoms. These may represent manifestations of a cytokine storm that is triggered by unknown antecedents. Instruments to measure flare such as the OMERACT PFQs have been very recently developed and validated to provide a new opportunity to correlate molecular findings with clinical signs and symptoms of flare. Patients managed with TNF inhibitors who discontinue the medication perioperatively are most likely to be at increased risk for flare and provide a unique opportunity to study the biology of flare in RA. The goal of this aim is to correlate the clinical phenotype as measured by the OMERACT PFQ, measured weekly with the immunological data. The immunological phenotype will be characterized using RNA sequencing of white blood cell (WBC) to develop a comprehensive molecular profile of RA flare.

Comparison of data collected in patients who flare versus those who do not flare provides a unique opportunity to characterize and understand flare, and define the significance of perioperative flare on arthroplasty and disease outcomes while providing further understanding of the biology and immunology of RA worsening.

2. Pincus T, Sokka T, Kautiainen H. Patients seen for standard rheumatoid arthritis care have significantly better articular, radiographic, laboratory, and functional

status in 2000 than in 1985. *Arthritis Rheum* 2005; Apr;52(4):1009-19.

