8. ESR
9. CRP
10. ACPA status
11. RF status
12. Intra-op steroids: yes/no
13. Metal implants?
14. MD 28 joint count
15. MD Global
16. NSAID status

17. Opioid use
18. Current steroid use
19. Current methotrexate use
20. Current non-MTX DMARD use
21. Current biologic use
22. Current statin use
23. Current ACE inhibitor use
24. Current ARB inhibitor use
25. Therapies that have been tried & stopped

COORDINATOR OFFICE VISIT FOLLOW-UP

New form location

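### Aims 5 and 6 compare biomarkers between flarers and non-flarers without adjustment, although the plan expects the groups to differ in biologic withdrawal; a drug-state difference could be read as flare biology.

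*Combined protocol and SAP*

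**What the plan says.** The analysis of aims 5 and 6 is in Sample Size and Data Analysis (view 2.11.1), item 3.0:

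- Group comparison: "we will compare levels of serum and tissue biomarkers between RA who flare and RA who do not flare using T-tests or chi-square tests".
- Association: "We will correlate self-report functional scores and biomarkers with the development of flare using Spearman correlations".
- Sequencing: "The raw read counts will then be processed with one of the Bioconductor package for Differential Gene expression (DESeq, edgeR, or limma/voom"). No design formula or covariate is given.

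Other sections link drug state to the comparison groups:

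- Hypothesis 3 (Specific Aims, item 3.0) says that flarers "more likely will have had a history of withdrawing a biological therapy compared to patients who do not flare".
- Background (view 2.1, item 2.0) says that "Patients managed with TNF inhibitors who discontinue the medication perioperatively are most likely to be at increased risk for flare", and that biologics are stopped around surgery to limit infection.
- In the flare definition (Specific Aims, item 2.0, aim 1), one qualifying criterion is "patient wants/needs retreatment of DMARDs and/or biologics and/or prednisone increase".

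Adjustment appears elsewhere in item 3.0. Aim 2 has an exploratory look at long-term scores and biomarkers, "adjusting for unknown confounders including baseline function, age, sex, and co-morbidity score". Aim 3 plans a generalized estimating equation for predictors of flare, with a similar list. Neither list names a drug. The coordinator intake form (view 2.7) records "Current biologic use" as well as steroid, methotrexate and other DMARD use, and the follow-up form repeats these items.

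**The concern.** The markers in aim 5 (ROCK, the IRFs and their inhibitors) are chosen because they measure immune activation, and biologics and steroids plausibly change immune activation. If the flare group contains more patients who stopped a biologic, the two groups would differ in these markers even if flare had nothing to do with them. An unadjusted comparison cannot tell the two explanations apart.

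The application form asks how confounders will be identified and handled. For aims 5 and 6 that is not answered, although the relevant drug data are collected. At stake is the reading of Hypothesis 5 and of the gene-expression results: a signature of drug withdrawal could be carried forward as a candidate signature of flare.

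**Working it through.** **The plan's own figures.** The documents give no sample size or power for aims 5 and 6. The only stated calculation is for the primary flare rate: exact binomial test, 0.26 versus 0.10, N = 47, power 0.8143, actual alpha 0.0445. Placing at most 0.025 in each tail reproduces both values. This confirms the 47 but does not bear on the biomarker tests.

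**Group sizes.** 0.26 × 47 = 12.2, so about 12 flarers and 35 non-flarers. With that split a two-sided t-test has 80% power only for a difference of about 0.96 SD.

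**Assumed inputs (not in the documents).** The proportion exposed to the drug state is p_F in flarers and p_N in non-flarers. The drug state shifts the marker by δ SD. Flare itself has no effect.

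**Formulas.**

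- Spurious difference = δ(p_F − p_N).
- Variance within a group = 1 + δ²p(1 − p).
- SE = √(V_F/12 + V_N/35).
- Rejection rate ≈ P(Z > 1.96 − z) + P(Z < −1.96 − z), where z = spurious difference / SE.

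**Worked case: 70% versus 30%, δ = 1.** The difference is 1 × 0.40 = 0.40. V = 1 + 0.21 = 1.21 in both groups. SE = √(1.21/12 + 1.21/35) = 0.368, so z = 1.087 and the rejection rate is about 19%.

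| Exposed, flare / non-flare | δ (SD) | Spurious difference (SD) | Formula | Simulated t-test |
|---|---|---|---|---|
| 60% / 30% | 0.5 | 0.15 | 7.2% | 6.7% |
| 60% / 30% | 1.0 | 0.30 | 12.8% | 13.2% |
| 70% / 30% | 1.0 | 0.40 | 19.2% | 18.5% |
| 70% / 30% | 1.5 | 0.60 | 31.5% | 31.5% |

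The simulation used 8,000 replicates per row, and a re-run gave 6.8%, 13.6%, 19.1% and 31.2%. With a term for the drug state that drives the shift, the simulated rejection rate is 4.6% to 5.6%. With equal exposure (60% in both groups) the unadjusted test is also at about 5%, so the excess comes from the imbalance.

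**Other inputs.** A separate simulation at 12 versus 35, with exposure from 70/50% to 90/30% and δ of 0.5 or 1.0, gave 5.8% to 35.9% unadjusted.

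**Larger samples do not help.** At the maximum enrolment of 200, if all were RA patients, the split is 52 versus 148. The first three rows of the table then become about 14%, 39% and 61%.

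**Why week-6 drug status is not the right adjuster.** Suppose withdrawal drives the marker (70% versus 30%, δ = 1) and the model adjusts for current use at week 6. The false-positive rate falls from 19% to 12% if half of those who withdrew have restarted, to 7% if 80% have, and stays at 19% if none have. Suppose instead that flare has a true 1 SD effect and week-6 steroid use is 80% in flarers and 20% in non-flarers. Adjusting for that use then cuts power from 83% to 67%. These rates are also assumptions.

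**The case against.** The strongest reply has four parts.

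**Adjustment is not absent from the plan.** Aim 2 includes an adjusted look at biomarkers, and aim 3 models predictors of flare, among which the aims list ROCK-pathway biomarkers. Both covariate lists are open-ended. This stands, and a reader who infers that biomarkers are never analysed with adjustment would be wrong. What remains is that no list names a drug and that the stated tests for aims 5 and 6 have no covariates. For RNA sequencing, the packages accept covariates, so adjustment there is unspecified rather than excluded.

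**The expected imbalance is narrower than it may seem.** A reader might infer that the plan predicts a difference in drug use generally. Hypothesis 3 speaks only of having withdrawn a biologic. The weekly aim 6 samples come from a subset limited to patients who withdrew biologics, so the imbalance is smaller there. Aim 5 is worded as a change from baseline, in which constant drug differences cancel; the simulation models a single level and so does not measure the bias in a change. A change score does not remove the effect of drugs stopped or restarted between the two draws, and the analysis text speaks of levels.

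**Adjustment can do harm.** Stopping a biologic may lead to flare through immune activation, in which case adjusting removes part of the signal sought. Retreatment by week 6 can result from the flare or form part of its definition. This stands and determines the fix: adjusting for drug status at each draw would not cure the week-6 comparison.

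**The stakes are limited.** A reader might infer that Hypothesis 5 would be wrongly declared proven. The documents do not support that: all secondary outcomes are labelled exploratory, no decision rule is attached to Hypothesis 5, and the Background says that validation would need a larger study.

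**Conclusion.** The concern holds for the surgery-sample comparisons (blood and tissue) and for the week-6 blood comparison. The plan predicts an imbalance in biologic withdrawal between the groups, tests immune markers without adjustment, and leaves drug exposure out of its named covariates.

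The size, about 7% to 31% against 5%, depends wholly on the assumed imbalance and drug effect. At the low end it is close to nominal. It describes confounding by a drug state that precedes the flare, in a comparison of levels. At week 6 the bias can go either way, because withdrawal could mimic activation while retreatment before the draw could mask it.

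The return to about 5% assumes that the model contains the drug state that matters. Pre-operative biologic use is a reasonable stand-in for withdrawal because the Background says that biologics are stopped around surgery, but it is not identical to it, so some confounding may remain. The harm is to the interpretation of exploratory findings; the primary flare rate is unaffected.

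**What to change.** In Data Analysis, aims 5 and 6:

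1. Replace the t-test with a linear model of the (log) marker on flare, pre-operative biologic use and pre-operative systemic steroid use, both from the intake form. Use the same pre-operative terms for the surgery and week-6 samples.
2. For the week-6 comparison, add the baseline level of the marker.
3. Put the same pre-operative terms into the RNA-sequencing design.
4. Report the unadjusted difference beside each adjusted one, and label any remaining chi-square or Spearman result as unadjusted.
5. Keep week-6 drug status out of the main model. Use it only in a labelled sensitivity analysis, for example one stratified by retreatment before the week-6 draw.
6. Define pre-operative biologic use as use before the perioperative stop, since some patients are enrolled on the day of surgery.

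The cost is SAP wording, with no new data items. The model spends two degrees of freedom on drug terms (three with the baseline marker), and intervals will be somewhat wider. If withdrawal acts on flare through the marker, the adjusted estimate will be attenuated, which is why both estimates are shown.
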